### 3.3. Benefit/Risk Assessment

The most common safety issue with administration of tirzepatide was related to frequent reporting of decreased appetite and GI side effects, most commonly nausea, vomiting, and diarrhea. These GI events were generally mild in severity, with few moderate, and no severe events reported in Phase 1 studies. Tirzepatide triggered generation of ADAs in a subset of

patients in Phase 2 trials. The presence of tirzepatide ADA did not affect PK or pharmacodynamic (PD) parameters, and was not associated with increased incidence of local or systemic hypersensitivity AEs in Phase 1 and Phase 2 studies up to 26 weeks of exposure. Based on these results, tirzepatide ADA represents a low risk in exposed patients, but more data is needed for definitive conclusion on the frequency and severity of possible side effects. No other clinically relevant safety concerns were identified in the dose range up to 15 mg, the highest dose investigated in Phase 1 and Phase 2 studies in T2DM patients, administered QW up to 26 weeks. Findings to date indicate that the safety profile for a dual GIPRA/GLP-1RA is similar to the safety profile of the selective GLP-1RAs. Potential risks, such as GI effects, acute pancreatitis, increases in heart rate, and hypoglycemic events are consistent with the risks associated with currently available long-acting GLP-1RAs. To mitigate the risk of GI side effects, tirzepatide 15 mg will be attained via step-wise dose escalation. Details on the management of these AEs are provided in Section 7.7.1 (Management of Subjects with Gastrointestinal Symptoms). The monitoring plan for all AEs of special interest is included in this protocol, as well as treatment measures, when appropriate.

Since Study GPGU will enroll subjects without diabetes, no self-monitoring of plasma glucose (PG) is planned. Consistent with the mechanism of action of incretins, which are nonsecretagogues, severe hypoglycemia has not been reported in Phase 1 or Phase 2 trials that included healthy subjects or patients with T2DM. However, to mitigate the risk, the subjects in this study will be trained on signs and symptoms of hypoglycemia and self-treatment measures. Section 9.2.2.1 (Hypoglycemia) describes definitions and criteria when diagnosing and categorizing an episode considered to be related to hypoglycemia. Section 7.4.1.1 (Management of Hypoglycemia) provides detailed information concerning the management of hypoglycaemia.

There are several possible AEs associated with the planned procedures in the study. The respiratory chamber will be used to obtain parameters needed to calculate respiratory quotient (RQ), EE, and substrate oxidation rates (see [Appendix 6](#) for details). Some level of claustrophobia or discomfort may be experienced from staying in the respiratory chamber and being continuously monitored by a camera. The dual energy X-ray absorptiometry (DXA) scan will be used to measure the amount of bone, muscle, and fat in the body. Subjects may be exposed to a small amount of radiation during the procedure. The radiation dose for a DXA scan is less than 1 mrem, which is less than a chest X-ray, or equal to about 12 hours of background radiation from the sun.

Subjects in Study GPGU are not expected to have direct health-related benefits. Potential risks described above, are considered to be transient and long-term health risks are low. The majority of these risks are clinically detectable and manageable, and will be monitored during the study.

More information about the known and expected benefits, risks, serious adverse events (SAEs) and reasonably anticipated AEs of tirzepatide are to be found in the Investigator's Brochure (IB). Information on AEs expected to be related to the investigational product (IP) can be found in Section 6 (Development Core Safety Information) of the IB. Information on SAEs that are expected in the study population independent of drug exposure will be assessed by the sponsor in

aggregate, periodically during the course of the study, and can be found in Section 5 (Effects in Humans) of the IB.

## 4. Objectives and Endpoints

Table GPGU.1 shows the objectives and endpoints of the study.

**Table GPGU.1. Objectives and Endpoints**

Objectives	Endpoints
Primary To assess the effect of tirzepatide versus placebo on SMR after 18 weeks ( $\pm 1$ week) of treatment	
 
The change from baseline to Week 18 in SMR, as measured in the respiratory chamber (whole-room calorimetry)
 

Secondary To assess the effect of tirzepatide versus placebo after 18 weeks ( $\pm 1$ week) of treatment: 
 
Appetite and food intake
 
Energy expenditure
 
Substrate oxidation rates
 
Body weight and body composition
 
Lipid metabolism
 
	
 
The change from baseline to Week 18 in appetite VAS
 
The change from baseline to Week 18 in food intake as assessed by ad libitum meal test
 
The change from baseline to Week 18 in 24-hour EE
 
The change from baseline to Week 18 in 24-hour RQ
 
The change from baseline to Week 18 in sleep RQ
 
The change from baseline to Week 18 in duration of periods with <math>RQ < 0.80</math>
 
The change from baseline to Week 18 in fat, protein, and carbohydrate oxidation
 
The change from baseline to Week 18 in BW
 
The change from baseline to Week 18 in body fat-free mass
 
The change from baseline to Week 18 in body fat mass
 
The change from baseline to Week 18 in the percentage of body fat mass
 
The change from baseline to Week 18 in triglycerides, cholesterol, LDL, VLDL, and HDL cholesterol, FFA, glycerol, 3-hydroxybutyrate, and acylcarnitines assessed during sMMTT
 
The change from baseline to Week 18 in ApoB-48, ApoB-100, ApoC-III, and LPL during sMMTT
 
The change from baseline to Week 18 in fasting concentration of leptin, adiponectin, IGFBP 1 and 2
 

Objectives	Endpoints
Secondary (continued) 
 
Insulin sensitivity
 
	
 
The change from baseline to Week 18 in fasting insulin resistance (as measured by the HOMA2 method [HOMA2-IR]) and postprandial insulin sensitivity indices (Matsuda, OGIS, and Stumvoll) assessed during sMMTT
 


 
Glucose control
 
	
 
The change from baseline to Week 18 in fasting and postmeal glucose during sMMTT
 
The change from baseline to Week 18 in hemoglobin A1c
 

Exploratory To assess the effect of tirzepatide versus placebo after 18 weeks ( $\pm 1$ week) of treatment: 
 
GIPR signaling, lipid metabolism, carbohydrate metabolism, and insulin signaling pathways in subcutaneous adipose tissue
 
	
 
The change from baseline to Week 18 in markers of GIPR signaling, lipid metabolism, carbohydrate metabolism, and insulin signaling pathways as measured in exploratory mRNA expression, lipidomics, metabolomics, or targeted protein assays of subcutaneous adipose tissue biopsy samples, receptor expression, signal transduction, and metabolic changes in adipose tissue
 

 
Safety and tolerability
 
	
 
Adverse events
 
Safety laboratory parameters
 
Frequency of treatment-emergent anti-tirzepatide antibodies
 
Treatment-emergent depression and suicidal ideation as assessed using C-SSRS and PHQ-9
 

Abbreviations: ApoB-48 = apolipoprotein B-48; ApoB-100 = apolipoprotein B-100; ApoC-III = apolipoprotein C-III; BW = body weight; C-SSRS = Columbia-Suicide Severity Rating Scale; EE = energy expenditure; FFA = free fatty acid; GIPR = glucose-dependent insulinotropic polypeptide receptor; HDL = high-density lipoprotein; HOMA2 = Homeostatic Model Assessment of Insulin Resistance; HOMA2-IR = insulin resistance as measured by the HOMA2 method; IGFBP = insulin-like growth factor binding protein; LDL = low-density lipoprotein; LPL = lipoprotein lipase; mRNA = messenger ribonucleic acid; OGIS = Oral Glucose Insulin Sensitivity; PHQ-9 = Patient Health Questionnaire-9; RQ = respiratory quotient; sMMTT = standardized mixed-meal tolerance test; SMR = sleep metabolic rate; VAS = visual analog scale; VLDL = very low-density lipoprotein.

## 5. Study Design

### 5.1. Overall Design

This is a Phase 1, single-center, randomized, sponsor (study team members directly involved in study management)-, investigator- and subject-blind, placebo-controlled, parallel-arm study in obese subjects. This study is designed to assess differences in the mechanisms of action with respect to energy balance, lipid and carbohydrate metabolism, and insulin sensitivity between tirzepatide and placebo, in combination with a low-calorie diet in non-diabetic, obese subjects. The primary objective of this study is to compare the 2 treatment groups for changes from baseline in sleep metabolic rate (SMR) after 18 weeks ( $\pm 1$  week) of treatment.

The subject will sign the informed consent form (ICF) before any study procedures are performed. Eligibility for this study will be assessed at screening (Visit 1) and confirmed at lead-in (Visit 2). Screening procedures will be performed within 4 weeks prior to lead-in, according to the Schedule of Activities (Section 2).

Eligible subjects will enter lead-in (Visit 2) within 2 weeks prior to randomization. Subjects will perform baseline assessments in the clinical research unit (CRU) prior to randomization, according to the Schedule of Activities (Section 2). After the completion of all baseline procedures, subjects will be randomized in a 1:1 ratio to tirzepatide or placebo.

Tirzepatide 15 mg will be attained via step-wise dose escalation to reduce the risk of GI AEs. Tirzepatide dosing will start at a dose of 2.5 mg QW for 2 weeks, followed by a step-wise dose escalation to 5 mg QW for 2 weeks, and 10 mg QW for 4 weeks, until the 15-mg QW dose is reached and maintained for the remainder of the treatment period (10 weeks  $\pm 1$  week). Subjects will return to the CRU every week for QW dose administration for 18 weeks ( $\pm 1$  week).

[figure not shown]
Subjects in both groups will receive a standardized dietary intervention to target a BW reduction of 10% ( $\pm 2\%$ ) after approximately 14 weeks of treatment. Between Week 14 and Week 18 ( $\pm 1$  week), dietary intervention will shift to promoting maintenance of 10% weight loss (Section 6.3.1) within target range prior to admission to the CRU and end-of-treatment procedures to assess primary and secondary objectives. Description of these procedures is provided in Section 2 (Schedule of Activities). Subjects will be readmitted to the CRU at Week 18 ( $\pm 1$  week) to perform end-of-treatment CRU study procedures. These CRU study procedures will be performed in all patients, irrespective of whether they reached their BW target or not, and according to the same schedule as during the lead-in period.

Section 2 (Schedule of Activities) presents all planned visits and procedures for this study. After the completion of the treatment period, a follow-up visit will be performed within 4 weeks of the last dose to assess subject safety and subsequently complete the subject's participation.

Study governance considerations are described in detail in [Appendix 3](#).

[Figure GPGU.1](#) illustrates the study design.

[figure not shown]
[Figure GPGU.2](#) illustrates the clinical research unit procedures.

Abbreviations: DXA = dual energy X-ray absorptiometry; FCI = Food Craving Inventory; FPQ = Food Preference Questionnaire; QW = once weekly; sMMTT = standardized mixed-meal tolerance test; VAS = visual analog scale.

Figure GPGU.1.

Illustration of study design for Protocol I8F-MC-GPGU.

Abbreviations: DXA = dual energy X-ray absorptiometry; FCI = Food Craving Inventory; FPQ = Food Preference Questionnaire; sMMTT = standardized mixed-meal tolerance test; VAS = visual analog scale.

**Figure GPGU.2. Illustration of clinical research unit procedures.**

## 5.2. Number of Participants

Up to 56 subjects may be enrolled (ie, randomized) to maximize the probability that approximately 46 subjects complete the study assuming a 15% discontinuation rate. For purposes of this study, a subject completes the treatment period when all scheduled procedures through Week 18 (Visit 20), as shown in Section 2 (Schedule of Activities), have been finished. A subject completes the study when all scheduled procedures through Week 22 (Visit 21) have been completed.

## 5.3. End of Study Definition

End of the study is the date of the last visit or last scheduled procedure shown in Section 2 (Schedule of Activities) for the last subject.

## 5.4. Scientific Rationale for Study Design

Study GPGU will employ a parallel-group design to minimize the confounding effects of changes in BW and, potentially, other metabolic parameters on the primary efficacy measure of SMR.

Placebo is chosen as the comparator to enable determination of the effect on parameters of energy balance (food intake and EE) attributable specifically to tirzepatide. An active GLP-1RA comparator was considered as unnecessary since the results of EE and substrate utilization studies showed no effect of selective GLP-1RAs on the outcomes of interest (van Can et al. 2014; Blundell et al. 2017).

The primary study measure SMR was chosen as the most reproducible measure of EE, since it is not influenced by activity or food intake.

The secondary study measures, such as other parameters of EE, appetite and food intake, substrate oxidation, BW and body composition, lipid metabolism, insulin sensitivity, and glucose control, are expected to provide important, additional data. All study measures and methods of assessment are well validated and fully established in the medical literature as the parameters and methods relevant for evaluation of objectives of Study GPGU. The timing of endpoint measurements (Week 18 [Visit 20]) was determined based on exposure response modeling of tirzepatide's effect on weight loss as observed in a Phase 2 clinical study (Frias et al. 2018).

To avoid the confounding effect of changes in glucose regulation on EE, the study will enroll nondiabetic, obese subjects, only. Subjects in both study groups will target same BW lowering range by means of a low-calorie diet to minimize the confounding effect of BW changes on the primary study measure. The weight loss target of 10% ( $\pm 2\%$ ) was chosen as it matches expected BW change with the 15-mg dose of tirzepatide at study endpoint, based on data from Phase 2 trials.

The dose justification for tirzepatide is provided in Section 5.5 (Justification of Dose).

The rationale for the sample size is provided in Section 10.1 (Sample Size Determination).

## 5.5. Justification for Dose

The tirzepatide dose of 15 mg administered SC QW is selected based on current preclinical pharmacology, toxicology, and clinical data, and is the highest maintenance dose planned for evaluation in the Phase 3 program.

The tirzepatide treatment period will consist of a step-wise dose escalation. Tirzepatide dosing will start at a low dose of 2.5 mg QW and will be escalated to 15 mg QW as described in Section 5.1 (Overall Study Design). The step-wise increments are based on cumulative understanding of safety and GI tolerability from Phase 1 and 2 studies and are expected to minimize GI tolerability concerns in this obese population by permitting adequate time for development of tolerance to GI events.

While a steeper dose escalation scheme with a higher starting dose of 5 mg, escalating to 15 mg within 7 weeks was previously implemented in Phase 2 and was found to be safe, this scheme was associated with some GI tolerability concerns.

To minimize the incidence of GI tolerability events, this study will employ a lower starting dose of 2.5 mg to initiate the dose escalation, permitting 8 weeks of step-wise dose escalation prior to attaining a maintenance dose of 15 mg at Week 9. Steady-state exposures are expected to be

attained within 4 weeks of starting 15 mg dose of tirzepatide. Treatment will be continued for 10 weeks ( $\pm 1$  week) after commencing the 15-mg maintenance dose.

Tirzepatide 15 mg is predicted to maintain an exposure multiple of 1.6 to 2.4 to the no-observed-adverse-effect level doses in 6-month monkey and rat toxicology studies, respectively. Additional information can be found in the IB.

## 6. Study Population

Eligibility of subjects for the study will be based on the results of screening medical history, physical examination, vital signs, clinical laboratory tests, and electrocardiograms (ECGs).

The nature of any conditions present at the time of the physical examination and any preexisting conditions will be documented.

Screening may occur within 4 weeks prior to lead-in. Eligible subjects will enter lead-in (Visit 2) within 2 weeks prior to randomization. Subjects who are not enrolled within 6 weeks of screening may be subjected to additional medical assessment and/or clinical measurements to confirm their eligibility.

Prospective approval of protocol deviations to recruitment and enrollment criteria, also known as protocol waivers or exemptions, are not permitted.

### 6.1. Inclusion Criteria

Subjects are eligible for inclusion in the study only if they meet all of the following criteria at screening:

#### Subject Characteristics

[1] Are obese (body mass index of 30 kg/m^2 to 45 kg/m^2, inclusive), and nondiabetic male or female subjects, as determined by medical history, physical examination, and laboratory assessments at screening, and have at least one of the following metabolic impairments (Alberti and Zimmet 1998; American Diabetes Association 2019; Grundy et al. 2005; Huang 2009; NIH [WWW]):

- Waist circumference  $\geq 102$  cm (40 inches) or  $\geq 88$  cm (35 inches) for males and females, respectively;
- High-density lipoprotein (HDL) cholesterol concentration  $< 50$  mg/dL for females and  $< 40$  mg/dL for males (or being on medicine to treat low HDL cholesterol);
- Serum triglycerides concentration  $\geq 150$  mg/dL or on medication to treat elevated triglycerides;
- Systolic blood pressure  $> 130$  mm Hg and/or diastolic blood pressure  $> 85$  mm Hg or already being treated with anti-hypertension medications;
- Impaired glucose tolerance defined as at least one of the following:
  - Fasting plasma glucose (PG)  $> 100$  mg/dL and  $< 125$  mg/dL;
  - Postglucose challenge PG (oral glucose tolerance test [OGTT])  $\geq 140$  mg/dL and  $< 200$  mg/dL;
  - Hemoglobin A1c between  $\geq 5.7\%$  and  $< 6.5\%$ ;

- Insulin resistance as measured by the Homeostatic Model Assessment of Insulin Resistance (HOMA2-IR)  $>1.8$  (Matthews et al. 1985; Levy et al. 1998);
- [2] Must be weight stable (no dietary weight loss/gain greater than 3 kg) in the last 1 month;
- [3] Have safety laboratory test results within normal reference range or with abnormalities deemed clinically insignificant by the investigator;
- [4] Have venous access sufficient to allow for blood sampling as per the protocol;
- [5] Male or female subjects between the ages of 18 to 60 years, inclusive;

[5a] Male subjects:

- Men, regardless of their fertility status, with nonpregnant woman of childbearing potential (WOCBP) partners must agree to either remain abstinent (if this is their preferred and usual lifestyle) or use condoms as well as 1 additional highly effective (less than 1% failure rate) method of contraception (such as combination oral contraceptives, implanted contraceptives, or intrauterine devices) or effective method of contraception (such as diaphragms with spermicide or cervical sponges) for the duration of the study and until their plasma concentrations are below the level that could result in a relevant potential exposure to a possible fetus, predicted to be 90 days.
  - Men and their partners may choose to use a double-barrier method of contraception. (Barrier protection methods without concomitant use of a spermicide are not an effective or acceptable method of contraception. Thus, each barrier method must include use of a spermicide. It should be noted however that the use of male and female condoms as a double-barrier method is not considered acceptable due to the high failure rate when these barrier methods are combined).
  - Periodic abstinence (eg, calendar, ovulation, symptothermal, postovulation methods), declaration of abstinence just for the duration of a study, and withdrawal are not acceptable methods of contraception.
- Men with pregnant partners should use condoms during intercourse for the duration of the study and until the end of estimated relevant potential exposure in WOCBP (90 days).
- Men must agree to refrain from sperm donation for the duration of the study and until their plasma concentrations are below the level that could result in a relevant potential exposure to a possible fetus, predicted to be 90 days following last dose of investigational product (IP).

- Men who are in exclusively same-sex relationships (as their preferred and usual lifestyle) are not required to use contraception.

[5b] Female subjects:

- Women of childbearing potential who are abstinent (if this is complete abstinence, as their preferred and usual lifestyle) or in a same-sex relationship (as part of their preferred and usual lifestyle) must agree to either remain abstinent or stay in a same sex relationship without sexual relationships with males. Periodic abstinence (eg, calendar, ovulation, symptothermal, postovulation methods), declaration of abstinence just for the duration of a study, and withdrawal are not acceptable methods of contraception.
- Otherwise, WOCBP participating must agree to use effective contraception, (see contraception guidance below), for the entirety of the study. Contraception must continue following completion of IP administration for 30 days.
  - Women of child-bearing potential participating must test negative for pregnancy prior to initiation of treatment as indicated by a negative serum pregnancy test at the screening visit followed by a negative urine pregnancy test within 48 hours prior to exposure and at other times as specified in Section 2 (Schedule of Activities).
  - Two forms of effective contraception, where at least 1 form is highly effective (less than 1% failure rate, such as combination oral contraceptives, implanted contraceptives or intrauterine devices) will be used. Effective contraception (such as male or female condoms with spermicide, diaphragms with spermicide or cervical sponges) may be used as the second therapy. Barrier protection methods without concomitant use of a spermicide are not a reliable or acceptable method. Thus, each barrier method must include use of a spermicide (that is, condom with spermicide, diaphragm with spermicide, female condom with spermicide). It should be noted that the use of male and female condoms as a double barrier method is not considered acceptable due to the high failure rate when these methods are combined.
- Women who are not of childbearing potential may participate and include those who are:
  - Infertile due to surgical sterilization (hysterectomy, bilateral oophorectomy, or tubal ligation), congenital anomaly such as mullerian agenesis, or

- Postmenopausal – defined as either
  - i. A woman at least 50 years of age with an intact uterus, not on hormone therapy, who has had either
    - a) cessation of menses for at least 1 year, or
    - b) at least 6 months of spontaneous amenorrhea with a follicle-stimulating hormone >40 mIU/mL; or
  - ii. A woman 55 or older not on hormone therapy, who has had at least 6 months of spontaneous amenorrhea; or
  - iii. A woman at least 55 years of age with a diagnosis of menopause prior to starting hormone replacement therapy.

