Insulin, leptin, adiponectin, IGFBP 1, IGFBP 2			X				See Appendix 6, Table GPGU.4 for sampling details.
Glucose			X				See Appendix 6, Table GPGU.4 for sampling details.
Lipid panel:							See Appendix 6, Table GPGU.4 for sampling details.
• Triglycerides, total cholesterol							
• LDL-C, VLDL-C, HDL-C							
• ApoB-48, ApoB-100, ApoC-III							
• LPL							
FFA, glycerol, 3-hydroxybutyrate, acylcarnitine			X				
OGTT	X						To determine subject eligibility per requirements listed in Section 6.1 (Inclusion Criteria), OGTT will be performed (see Appendix 6 for details).
Pregnancy test	X		X				For women of childbearing potential, a serum pregnancy test will be performed at screening. Urine pregnancy test will be performed on Day -4.
Investigative Tests							

Procedure	Screening	Lead-In					Comments
Visit	1*	2					
Week of Treatment	-6 to -2	-2 to -1					Week of treatment should be established versus the day of randomization (end of lead-in).
Study Day	-42 to -14	Any time from Day -14 to Day-1					
		-5	-4	-3	-2	-1	
Appetite (VAS), ad libitum food intake test			X				See Appendix 6 for details.
Retrospective VAS				X			See Appendix 6 for details.
Food craving inventory and food preference questionnaire				X			See Appendix 6 for details.
Adipose tissue biopsy (abdominal)						X	Sample will be collected outside of the respiratory chamber. See Appendix 6 for details.
Respiratory chamber				X	X	X	Approximately 2 × 23 hours from Day -3 to Day -1. See Appendix 6 for details.
sMMTT			X				See Appendix 6 for details of the procedure and sampling schedule.
DXA scan				X			See Appendix 6 for details. The predose DXA scan may be scheduled any time from Day -5 to Day -1.

\*Screening activities on Visit 1 may be performed over more than 1 day if necessary to fit subject and site scheduling.

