Respiratory chamber					X	X	X			Approximately 2 × 23 hours from Days 123 to 125. See Appendix 6 for details.
sMMTT				X						See Appendix 6 for details on the procedures and sampling schedule.
DXA scan					X					See Appendix 6 for details. The postdose DXA scan may be scheduled any time from Day 123 to 125.
Diagnostics										

Procedure	Treatment								Follow-up/ET	Comments
Visit	18	19	20	20	20	20	20	20	21	
Week of Treatment	16	17	18	18	18	18	18	18	22	
Study Day	106 ±1	113 ±1	120 ±7	121	122	123	124	125	Within 4 weeks after last dose	
PK samples			P						X	Immunogenicity / PK sampling times must be time-matched as much as possible.
Immunogenicity			P						X	
Nonpharmacogenetic stored samples			P						X	Fasting samples.

Abbreviations: AEs = adverse events; ApoB-48 = apolipoprotein B-48; ApoB-100 = apolipoprotein B-100; ApoC-III = apolipoprotein C-III; BP = blood pressure; CRU = clinical research unit; C-SSRS = Columbia-Suicide Severity Rating Scale; DXA = dual energy X-ray absorptiometry; ECG = electrocardiogram; ET = early termination; FFA = free fatty acid; HDL-C = high-density lipoprotein cholesterol; IGFBP = insulin-like growth factor binding protein; LDL-C = low-density lipoprotein cholesterol; LPL = lipoprotein lipase; OGTT = oral glucose tolerance test; P = predose; PD = pharmacodynamics; PHQ-9 = Patient Health Questionnaire-9; PK = pharmacokinetics; PR = pulse rate; SHFF = Self-Harm Follow-Up Form; SHSF = Self-Harm Supplementary Form; sMMTT = standard mixed-meal tolerance test; VAS = visual analog scale; VLDL-C = very low-density lipoprotein cholesterol.

Note: If multiple procedures take place at the same time point, the following order of assessments should be used: Vital signs, ECG, PD, PK, immunogenicity, safety laboratory, storage samples.

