## 9. Study Assessments and Procedures

Section 2 lists the Schedule of Activities, detailing the study procedures and their timing (including tolerance limits for timing).

[Appendix 2](#) lists the laboratory tests that will be performed for this study.

[Appendix 5](#) provides a summary of the approximate number and volume of invasive samples, for all sampling, during the study.

The specifications in this protocol for the timings of safety and sample collections are given as targets to be achieved within reasonable limits. Modifications may be made to the time points based upon emerging clinical information. The scheduled time points may be subject to minor alterations; however, the actual time must be recorded correctly in the eCRF. Failure or delays (ie, outside stipulated time allowances) in performing procedures or obtaining samples due to legitimate clinical issues (eg, equipment technical problems, venous access difficulty, or subject defaulting or turning up late on an agreed scheduled procedure) will not be considered as protocol deviations but the CRU will still be required to notify the sponsor in writing via a file note.

Unless otherwise stated in subsections below, all samples collected for specified laboratory tests will be destroyed within 60 days of receipt of confirmed test results. Certain samples may be retained for a longer period, if necessary, to comply with applicable laws, regulations, or laboratory certification standards.

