### Safety Laboratory Tests

Hematology	Clinical Chemistry
Hematocrit	Sodium
Hemoglobin	Potassium
Erythrocyte count (RBC)	Bicarbonate
Mean cell volume	Chloride
Mean cell hemoglobin	Calcium
Mean cell hemoglobin concentration	Phosphorus
Leukocytes (WBC)	Glucose (fasting)
Absolute counts of:	Blood urea nitrogen
Neutrophils	Uric acid
Lymphocytes	Total protein
Monocytes	Albumin
Eosinophils	Total bilirubin
Basophils	Alkaline phosphatase
Platelets	Alanine aminotransferase
	Aspartate aminotransferase
	Creatinine
	Lipase (fasting)
	Amylase
Urinalysis	Triglyceride b
Specific gravity	Total cholesterol b
pH	Hemoglobin A1c
Protein	
Glucose	
Ketones	
Bilirubin	
Urobilinogen	
Blood	
Leukocytes	
Microscopy a	
	Endocrine
	Follicle-stimulating hormone a
	Calcitonin
	Serologyc
	Hepatitis B surface antigen
	Hepatitis C antibody, hepatitis C RNA d
	HIV antibody
	Pregnancy test (urine, serum) e
	Drug and alcohol screen f

Abbreviations: HIV = human immunodeficiency virus; RBC = red blood cells; WBC = white blood cells.

Note: Results of these assays will be validated by the central or local laboratory at the time of testing. Additional tests may be performed or auto-calculated by the laboratory as part of its standard panel that cannot be removed. Some of the above parameters are calculated from measured values. Omission of calculated values will not be considered as a protocol violation.

a If clinically indicated, per investigator's discretion.

b Triglyceride and total cholesterol concentrations in the safety panel will not be required on the days that the lipid panel is performed.

c At screening only (unless previously performed within the last 6 months with reports available for review).

d See exclusion criteria (Section 6.2) for further details.

- e Pregnancy tests will be performed for women of childbearing potential. Serum pregnancy test is done at screening and follow-up and urine pregnancy is performed on Day -4 and Day 122.
- f Performed at screening. Procedures may be repeated throughout the study as deemed necessary by the investigator.

---

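### Criterion [5b] requires a negative urine pregnancy test in the 48 hours before first dose, but the only pre-dose urine test is scheduled on Day -4, at least 72 hours before dosing

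*Protocol*

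**What the plan says.** Protocol Section 6.1, criterion [5b], sets two conditions on women of childbearing potential before treatment starts: a negative serum pregnancy test at screening, then a "negative urine pregnancy test within 48 hours prior to exposure". It adds that testing also takes place at the other times listed in Section 2.

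The Screening and Lead-In table in Section 2 gives the serum test at screening and states: "Urine pregnancy test will be performed on Day -4". Appendix 2, footnote e, repeats this independently: "urine pregnancy is performed on Day -4 and Day 122". The Treatment Period table shows the first administration of study drug at Visit 3, Study Day 1, and has no pregnancy-test row. The next scheduled pregnancy test is the one on Day 122.

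Section 6 says that prospective deviations from the enrollment criteria, "also known as protocol waivers or exemptions, are not permitted". Section 9 allows some latitude on timing: "The scheduled time points may be subject to minor alterations".

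**The concern.** The eligibility criterion and the two operational sections do not match. The criterion ties the urine test to first exposure with a 48-hour limit. The schedule and the laboratory appendix, from which a site books its procedures, contain no test inside that limit.

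A site that follows Section 2 and Appendix 2 exactly would dose women of childbearing potential without having met [5b]. A site that notices [5b] must add a test that appears nowhere in its schedule. In the first case each such woman would, read literally, have been enrolled without meeting a criterion. Section 8.1.3 would then call for a discussion between sponsor and investigator, and documented approval for her to continue. The safety purpose of the rule, a recent negative test before exposure to the study drug, would also be weakened.

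**Working it through.** **Inputs**

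- Limit: 48 hours before first exposure (Section 6.1, [5b]).
- Scheduled pre-dose urine test: Day -4 only (Section 2 lead-in table; Appendix 2 footnote e).
- First dose: Day 1, with no visit window; the ±1 day windows begin at Day 8 (Section 2, Treatment Period table).
- Day numbering: the tables go from Day -1 to Day 1, with no Day 0.
- Randomization: Day -1, at the end of lead-in (Section 2; SAP Section 5.1).

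**Formula.** If the test and the dose are *d* calendar days apart, the gap is 24*d* hours at equal clock times, more than 24(*d* − 1) hours at its shortest, and less than 24(*d* + 1) hours at its longest.

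| Test day | *d* to Day 1 | Shortest (h) | Equal clock times (h) | Longest (h) | Always within 48 h? |
|---|---|---|---|---|---|
| Day -4 | 4 | more than 72 | 96 | less than 120 | Never within |
| Day -3 | 3 | more than 48 | 72 | less than 96 | Never within |
| Day -2 | 2 | more than 24 | 48 | less than 72 | Not guaranteed |
| Day -1 | 1 | more than 0 | 24 | less than 48 | Yes |

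The 72-hour lower bound for Day -4 is the three full days between the end of Day -4 and the start of Day 1 (Days -3, -2 and -1): 3 × 24 = 72. If a Day 0 were counted, the Day -4 gap would grow to 120 hours at equal clock times and more than 96 hours at its shortest. The mismatch therefore does not depend on the numbering.

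**Does other text supply the missing test?** The closing words of [5b] add the Section 2 times to the 48-hour test; they do not replace it, and Section 2 lists no such test. The Section 9 allowance covers minor shifts, whereas compliance would mean moving the test from Day -4 to Day -2 at the earliest. Where the lead-in table intends flexibility it says so, as in the scan row: "The predose DXA scan may be scheduled any time from Day -5 to Day -1". The pregnancy-test row has no such wording.

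**Should Day -4 simply be moved?** No. The baseline DXA scan is nominally on Day -3, and Section 3.3 notes: "Subjects may be exposed to a small amount of radiation during the procedure". The Day -4 test comes one day before that scan. Without it, the last pregnancy test before the scan would be the screening serum test, taken between Day -42 and Day -14: −3 − (−14) = 11 days to −3 − (−42) = 39 days earlier. Week 18 follows the same order, with a urine test on Day 122 and then the scan: "The postdose DXA scan may be scheduled any time from Day 123 to 125". This supports keeping Day -4 but is secondary. Section 3.3 puts the dose below 1 mrem, and a baseline scan moved to Day -5 would precede the Day -4 test anyway.

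**The case against.** The strongest reply is that nothing is missing from the plan. [5b] imposes the 48-hour test by itself, the Day -4 test does not forbid a later one, and a careful site that must confirm every criterion and has no waiver available would run it. On that view the fault is an incomplete schedule row, not two rules that cannot both be obeyed. This is fair as a description: the two can be reconciled by adding a test. It does not remove the fault, because a site that carries out the schedule and the appendix exactly as written fails the criterion.

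A second objection concerns the remedy. The lead-in header lets the study days fall between Day -14 and Day -1. If the whole block of columns could float, a test in the Day -1 column might also be more than 48 hours before dosing. The better reading is against this: the Day -1 column carries randomization, Section 2 counts treatment weeks from the day of randomization at the end of lead-in, Section 6.4 assigns subject numbers on Day -1, and SAP Section 5.1 places randomization on Day -1. Floating could in any case only lengthen the Day -4 gap. What stands is that stating the 48-hour limit in the schedule comment would be safer than a day label alone.

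Third, the protocol does not itself link pregnancy testing to the DXA scan. That is correct; the link is offered here only as a reason not to drop Day -4.

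**Conclusion.** The inconsistency is real. The only scheduled pre-dose urine test is nominally 96 hours and never less than 72 hours before first dose, against a limit of 48 hours. It is minor. The screening serum test, the inpatient Day -4 test and the contraception requirements remain, and nothing in the sample size, power or primary analysis depends on it. The documents do not say how many women of childbearing potential will be enrolled, so no number of affected subjects can be given. The conclusion that Day -4 is too early needs only a Day 1 dose. The conclusion that a Day -1 test always suffices also assumes that Day -1 and Day 1 are consecutive calendar days, as the schedule shows.

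**What to change.** Keep the 48-hour wording in [5b] and keep the Day -4 urine test. Add a urine pregnancy test on Day -1, after the subject leaves the respiratory chamber and before randomization:

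- Section 2, Screening and Lead-In: an X in the Day -1 column of the pregnancy-test row, and *Day -4 and Day -1* in its comment. Adding *the latter within 48 hours before first dose* would cover any shift in the calendar.
- Appendix 2, footnote e: *Day -4, Day -1 and Day 122*.

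Testing after chamber exit keeps the sample outside the urine collection used for urinary nitrogen (Appendix 6, Table GPGU.3, footnote b), and a positive result stops the subject before she is randomized. A pre-dose test on Day 1 would also meet the limit, but a positive result would then come after randomization. A Day -2 test would not guarantee compliance.

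The cost is one extra urine test per woman of childbearing potential, which [5b] already demands, during a stay that runs from admission on Day -5 to discharge on Day 1 (±1 day). The text changes are one table cell, one comment and one footnote. No visit or blood sample is added, and no existing test is removed.
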